7.9. Compensation for Participation

Participants will be compensated up to a total of \$455 for their time and effort according to the following schedule:

Initial screening visit:	\$20
Medical screening visit:	\$20
Medication Titration:	\$20
Initial Counseling Visit:	\$20
Brain Imaging Visit:	\$50 (if eligible)
Follow up visit week 2:	\$20
Follow up visit week 4:	\$20
Follow up visit week 6:	\$20
Follow up visit week 8:	\$20
Follow up visit week 10:	\$20
Follow up visit week 12:	\$50
Follow up visit week 16:	\$50

Follow up visit week 26: \$75

Completion bonus week 26*: \$50

*Only participants who have completed all 12 study visits will be eligible to receive the \$50 completion bonus.

In addition, participants will have the opportunity to earn up to \$5 additional at the initial screening visit for participating in snowball recruitment methods as described above. Participants who travel more than 10 miles from their home to attend visits on the UCLA campus will receive an additional \$10 per visit to cover travel costs. All participants will be provided with free parking validation or bus tokens for attendance to each study visit.

Female participants will receive an additional \$10 at each of the following visits for completing female-specific study procedures as described above: Medication Titration, FU week 4, FU week 8, FU week 12, FU week 16 and FU week 26, totaling \$410 for completion of all study procedures.

Participants are free to discontinue participation at any time and will receive compensation for the amount of time that they participated.

8. SAFETY MONITORING PLAN

Safety monitoring will be conducted throughout the study; therefore safety concerns will be identified by continuous review of the data by the PI and study physician, internal quality assurance monitor, and DSMB.

8.1. PI and Study Physician Safety Monitoring

Participants will be given a 24-hour telephone number for calling the physician to discuss side effects, and physician office hours will be available as needed. Adverse events, including side effects will be collected in an open-ended way at each study visit. Vital signs, weight, and neuropsychiatric side effects, including depression and suicidal ideation, will be monitored at each study visit. The study physician will repeat all the clinical labs at the week 12 follow-up in order to verify that there were no changes associated with the 12-week medication regimen (+ 2 week titration/stabilization period). In the event that significant medical problems are encountered, the blind will be broken and appropriate medical treatment will be provided.

8.2. Internal Quality Assurance Monitoring

The PI will designate appropriately qualified personnel to periodically perform quality assurance checks at mutually convenient times during and after the study. These monitoring visits provide the opportunity to evaluate the progress of the study and to obtain information about potential problems. The monitor will assure that data are accurate and in agreement with any paper source documentation used, verify that subjects' consent for study participation has been properly obtained and documented, confirm that research subjects entered into the study meet inclusion and exclusion

criteria, verify that study procedures are being conducted according to the protocol guidelines, monitor review AEs and SAEs, perform drug accountability, and assure that all essential documentation required by Good Clinical Practices (GCP) guidelines are appropriately filed. At the end of the study, they will confirm that the site has the appropriate essential documents on file, advise on storage of study records, and inspect the return and destruction records for unused study medication.

8.3. Data and Safety Monitoring Board (DSMB)

An independent DSMB of external advisors will meet prior to the start of the study, bi-annually during enrollment and follow-up and at trial end to review safety data. The Board will be blinded to subjects' actual randomized group assignments but may request at any time that the blind be broken by the data center, if concerns arise from the blinded data. In addition to bi-annual meetings, the DSMB will meet after half of the subjects (137) have been randomized to review safety data and the integrity of the study (i.e., an evaluation of the dropout rate and impact on the planned statistical analysis of the data) and make a formal recommendation to the PI on the continuation or early stopping of the study due to safety concerns. *Ad hoc* meetings will be convened if SAEs occur that are considered at least possibly related to the study medication.

9. ASSESSMENTS

All study assessments will be performed at the visits and time points outlined in the Schedule of Assessments (Appendix 2); the following sections outline the details and procedures associated with the assessments. Most assessments will be recorded directly into the EDC system (MediaLab) with the exception of a few, which will be completed first on paper, then entered into the database as noted below.

9.1. Adverse Events (AE) and Serious Adverse Events (SAE)

The study physician and study site staff are responsible for the detection, documentation, classification, reporting, and follow up of events meeting the definition of an AE or SAE. Adverse Events will be assessed at the medical screening visit and at each subsequent visit through the week 26 follow up visit. However, SAEs will be collected from the time of informed consent onward. General symptoms will be collected via an open ended question: "How have you been feeling since your last visit or the last time we spoke?"

Adverse Events will be recorded on the AE Log using accepted medical terms and/or the diagnoses that accurately characterize the event. When a diagnosis is known, the AE term recorded on the eCRF will be the diagnosis rather than a constellation of symptoms. The study physician will assess all AEs for seriousness, relationship to study medication, and severity. When an event has not resolved by study closure, it will be documented on the AE Log as "ongoing".

If a woman has a positive or borderline pregnancy test after enrollment, the pregnancy will be recorded as an AE. The site will contact the subject at least monthly and document the subject's status until the pregnancy has been terminated or completed. The outcome of the pregnancy (e.g., normal birth, death, abortion, congenital anomaly, or other disabling or life-threatening complication to the mother or newborn) will be recorded.

All AEs, including clinically significant abnormal findings on laboratory evaluations, regardless of severity, will be followed by study physicians until satisfactory resolution (the event either resolved or stabilized and is not expected to resolve in the near term). All SAE's will be reported per requirements.

9.1.1. Adverse Event (AE) Definition

An AE is any untoward medical occurrence in a participant who has been administered a pharmaceutical product and may not necessarily have a causal relationship with the administered treatment. An AE can therefore be any unfavorable and unintended sign (including a clinically significant laboratory abnormality), symptom, or disease temporally associated with the use of the study medication, whether or not related to the medication. Pre-existing conditions, diseases, or disorders are not considered AEs unless there is a change in severity or frequency.

9.1.1.1. *Classification of Adverse Event Intensity and Relationship to Study Medication*

For each recorded AE or SAE, the physician must make an assessment of severity based on the following criteria:

- **Mild:** *An event that is usually transient, requiring no special treatment, and does not generally interfere with the subject's daily activities.*
- **Moderate:** *An event that interferes with usual activities of daily living, causing discomfort but poses no significant or permanent risk of harm to the subject. The event is usually ameliorated with additional specific therapeutic intervention.*
- **Severe:** *An event that interrupts usual activities of daily living or significantly affects clinical status. The event poses a significant risk of harm to the subject and hospitalization may be required, and typically requires intensive therapeutic intervention.*
- **Life-threatening:** *An event that puts the subject into imminent risk of death without intervention.*

The physician must also make an assessment of relationship to the investigational product based on the following criteria:

- **Unrelated:** *The subject did not receive the investigational product, the temporal sequence of the AE/SAE onset relative to administration of the investigational product is not reasonable, or there is another obvious cause of the AE/SAE.*

- **Unlikely:** *There is evidence of exposure to the investigational product but there is another more likely cause of the AE/SAE.*
- **Possible:** *There is evidence of exposure to the investigational product, the temporal sequence of the AE/SAE onset relative to administration of the investigational product is reasonable, but the AE/SAE could have been due to another equally likely cause.*
- **Probable:** *There is evidence of exposure to the investigational product, the temporal sequence of the AE/SAE onset relative to administration of the investigational product is reasonable, and the AE/SAE is more likely explained by the investigational product than by any other cause.*
- **Definite** *There is evidence of exposure to the investigational product, the temporal sequence of the AE/SAE onset relative to administration of the investigational product is reasonable, the AE/SAE is more likely explained by the investigational product than by any other cause, and the AE/SAE shows a pattern consistent with previous knowledge of the investigational product or investigational product class.*

9.1.1.2. Outcomes and Actions Taken

All unresolved AEs will be followed for a minimum of 14 days (unless the AE is an ongoing pregnancy which must be followed to conclusion) after the subject's final study visit, unless the investigator's judgment dictates otherwise, the event has resolved or stabilized prior to the 14-day period, or the subject is lost to follow-up. Investigators are not obligated to actively seek AEs or SAEs in former study subjects that occur following the follow-up period.

For each recorded AE or SAE, the investigator must make an assessment of outcome at the time of last observation, as follows:

- **Fatal:** *The subject died.*
- **Resolved without Sequelae:** *The AE or SAE has ended.*
- **Resolved with Sequelae:** *The AE or SAE has ended but changes are noted from baseline.*
- **Unresolved – Ongoing:** *The AE has not ended and is ongoing at the end of the reporting period (i.e., 14 days after the final Follow-up visit) and the investigator deems that further follow up is not medically required*
- **Unknown – Lost to Follow-up:** *Lost to follow-up after repeated unsuccessful attempts to contact the subject.*

Actions taken with respect to study medication (discontinuation or not) will also be recorded. In addition, if the AE was treated (medications or other physical measures), this will also be recorded.

9.1.2. Serious Adverse Event (SAE) Definition

An SAE is any untoward medical occurrence that meets one of the following:

- Results in death
- Is life-threatening (at the time of the event)
- Requires inpatient hospitalization or prolongation of existing hospitalization
- Results in persistent or significant disability/incapacity
- Is a congenital anomaly/birth defect

A serious and unexpected AE is an SAE that is not identified in nature, intensity, or frequency in the risk information included in the Product Label for the drug. Important medical events that may not result in death, be life-threatening, or require hospitalization may be considered a serious adverse event when, based upon appropriate medical judgment, they may jeopardize the study subject and may require medical or surgical intervention to prevent one of the outcomes listed in the definition.

9.2. Alcohol Consumption Questionnaire (ACQ)

The Alcohol Consumption Questionnaire is measured with nine items assessing lifetime drinking history such as current drinking, age of onset, and attempts to quit/reduce drinking. This assessment will be completed directly by the participant at the initial screening visit.

9.3. Alcohol Use Disorders Identification Test (AUDIT)

The Alcohol Use Disorders Identification Test is used to identify persons with hazardous and harmful patterns of alcohol consumption. The AUDIT was developed by the World Health Organization (WHO) as a simple method of screening for excessive drinking. The AUDIT is a self-report measure that will be completed by the participant in MediaLab at the initial screening visit.

9.4. Barratt Impulsivity Scale (BIS-11)

The BIS-11 is a widely used measure of impulsiveness that includes 30 self-reported items that are scored to yield six first-order factors (attention, motor, self-control, cognitive complexity, perseverance, and cognitive instability impulsiveness) and three second-order factors (attentional, motor, and non-planning impulsiveness). This questionnaire will be completed by the participant electronically during screening and at each follow up visit.

9.5. Breathalyzer

An alcohol breathalyzer will be administered at consent, and at every in-clinic visit as a safety measure. BrAC must be equal to 0.000 prior to performing any study assessments. Results will be recorded on the paper checklist, and later entered into the database.

9.6. Clinical Laboratory Tests

Clinical laboratory tests, including a chemistry panel and liver function tests, will be performed at CTRC during the medical screening and week 12 follow up visits. The total blood volume to be collected is approximately 72 mL. Additional laboratory samples may be taken at the discretion of the study physician if the results of any tests fall outside reference ranges or clinical symptoms necessitate testing to ensure safety.

9.7. Clinical Institute Withdrawal Assessment for Alcohol (CIWA-Ar)

The CIWA-AR is a brief 10-item measure used to provide a quantitative index of the severity of the alcohol withdrawal syndrome. The CIWA-AR has been used both in clinical and research applications and has demonstrated both reliability and validity. This questionnaire will be administered on paper by appropriately trained staff during screening, at the medication titration visit, and at each follow-up visit. Participant responses will then be entered electronically.

9.8. Columbia Suicide Severity Rating Scale (C-SSRS)

The C-SSRS is a 4-page form asking questions about suicidal ideation, intensity of ideation, and suicidal behavior developed by Posner and collaborators at the New York State Psychiatric Institute. This scale is intended for use by trained administrators. The questions contained in the C-SSRS are suggested probes. Ultimately, the determination of the presence of suicidality depends on clinical judgment. Training is required before administering the C-SSRS through a 30-minute interactive slide presentation followed by a question-answer session through the Columbia University Medical Center. Those completing the training are certified to administer the C-SSRS, and will receive a training certificate. This scale will be used to assess current suicidal ideation at screening and at each follow up visit and will be administered by a trained staff member with responses recorded on paper first, then entered electronically.

9.9. Concomitant Medications

All medications taken by the participant 2-weeks prior to the start of screening and through the final follow-up contact at week 26 will be recorded. All medications reported by the participant will be recorded on a source document and later entered electronically.

9.10. Demographics

Demographics data include the participant's age, gender, race/ethnicity, marital status, education, employment pattern, occupation, and income level. These data will be collected by site staff at the initial screening visit on a source document and entered into an eCRF.

9.11. Drug Use Questionnaire (DUQ)

The Drug Use Questionnaire will collect information on frequency and quantity of drug use. Participants will directly enter responses into MediaLab at the initial screening visit.

9.12. Eating Disorders Inventory (EDI)

The EDI (Gerner, 1991) will be completed by all participants at the initial screening visit to assess for general weight concerns. Participants will directly enter responses into MediaLab.

9.13. EKG

A 12-lead resting ECG will be obtained at the medical screening visit. Any abnormalities will be noted and an assessment of clinical significance will be done by the study physician.

9.14. Alveolar Carbon Monoxide (CO) Levels

A Vitalograph CO monitor will be used to detect CO levels at screening to verify that participants are regular smokers and at follow up visits to assess for smoking abstinence. Test results will be recorded on the visit checklist and then entered into the database.

9.15. Fagerström Test for Nicotine Dependence (FTND)

The Fagerström Test for Nicotine Dependence will be used to assess smoking status and motivation to change smoking behavior at screening. This questionnaire will be completed by the subject electronically.

9.16. Family Tree Questionnaire (FTQ)

Information on family history of alcohol problems will be collected using the Family Tree Questionnaire. The questionnaire provides subjects with a family tree listing of relatives to identify blood relatives with alcohol problems. This questionnaire will be completed by the subject electronically at the initial screening visit.

9.17. Hospital Anxiety and Depression Scale (HADS)

The Hospital Anxiety and Depression Scale is a self-assessment tool to assess anxiety and depression levels. This measure will be completed at the initial screening visit and entered with participant responses entered directly into the database.

9.18. ImBIBe

ImBIBe is a 15-item questionnaire in which the subject responds on a 5-point scale responses to questions on the consequences of alcohol use. This scale was adapted from the Drinker Inventory of Consequences (Drinc) questionnaire based on FDA recommendations on patient reported outcomes. This questionnaire will be completed by the participant electronically.

9.19. Medical History

A Medical History interview will be conducted by the study physician at the medical screening visit and will screen for medical conditions that contraindicate taking naltrexone and/or varenicline.

9.20. Menstrual Cycle Calendar

The Menstrual Cycle Calendar (Roche and King, 2015) is a calendar-based interview will estimate recent dates of menstruation, determine average menstrual cycle length, and estimate the onset of next menses. It will be administered to female participants at the medication-titration visit and follow-up visits at week 4, 8, 12, 16 and 26.

9.21. Menstrual Distress Questionnaire (MDQ)

The MDQ (Moos, 1968) will assess the level of menstrual cycle distress female participants of child-bearing potential experienced during their most recent cycle. This questionnaire will be completed by female participants at the medication titration visit, and at the week 4, week 8, week 12, week 16 and week 2 follow-up visits.

9.22. Minnesota Nicotine Withdrawal Scale (MNWS)

The Minnesota Nicotine Withdrawal Scale assesses signs and symptoms of nicotine withdrawal. The participant will respond to this 9-item assessment at the initial screening visit and all follow up visits.

9.23. Morisky Medication Adherence Questionnaire (MAQ)

The Morisky Medication Adherence Scale (MMAS) is a generic self-reported, medication-taking behavior scale, validated for hypertension but used for a wide variety of medical conditions. It consists of four items with a scoring scheme of “Yes” = 0 and “No” = 1. The items are summed to give a range of scores from low adherence to high adherence. This measure will be completed by the participant at the initial screening visit and at each of the medication follow up visits.

9.24. Opioid Receptor Antagonist Scale

Women will complete an opioid receptor antagonist-specific adverse effect scale that has been previously shown to be related to menstrual cycle related distress and

response to naltrexone (Epstein and King 2004; Roche et al., 2015). This measure will be completed at the medication titration, week 4, 8, 12, 16 and 26 visits.

9.25. Ovulation Predictor Test

A one step ovulation urine test will be used to determine when there is a surge in the (LH) luteinizing hormone, which will inform where female participants are in their menstrual cycle. This measure will be completed at the medication titration, week 4, 8, 12, 16 and 26 visits.

9.26. Penn Alcohol Craving Scale (PACS)

The PACS is a five-item, self-report measure that includes questions about the frequency, intensity, and duration of craving, the ability to resist drinking, and asks for an overall rating of craving for alcohol for the previous week. Each question is scaled from 0 to 6. Participants will complete this scale at initial screening and at each follow up visit.

9.27. Physical Exam

A physical examination of the oral cavity, head, eyes, ears, nose, and throat, cardiovascular system, lungs, abdomen, extremities, skin, neuropsychiatric mental status and sensory/motor status, musculoskeletal system and general appearance will be performed during the medical screening visit. Abnormal findings will be reported as AEs, if appropriate.

9.28. Positive and Negative Affect Scale (PANAS)

The Positive and Negative Affect Scale comprises two mood scales, one that measures positive affect and the other which measures negative affect. The scale consists of 20 items using a 5-point scale that ranges from very slightly or not at all (1) to extremely (5). Participants will completed the PANAS initial screening and all follow up visits.

9.29. Pregnancy and Birth Control Assessment

An FDA approved rapid result urine pregnancy test will be used (i.e., dipstick test). If applicable, participants will be asked to sign a release of information form for study personnel to access medical records to obtain information regarding the outcome of a pregnancy that occurred during the study. The Birth Control Assessment is designed to determine a female subject's compliance with the birth control specifications detailed in the inclusion criteria. The Pregnancy and Birth Control Assessment will be completed at the initial screening visit, the medication titration visit, and at the 4, 8 and 12 week follow up visits.

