4. STUDY DESIGN

This study is a double-blind, randomized clinical trial using a two group medication design consisting of the combination of VAR (1 mg twice daily) + NTX (50 mg once daily) and VAR (1 mg twice daily) + PLA (matched to NTX), for smoking cessation in a sample of heavy drinking daily smokers who want to quit smoking and reduce drinking.

All participants will be daily smokers (≥ 5 cig/day) who are also heavy drinkers according to the National Institute on Alcohol Abuse and Alcoholism (NIAAA) guidelines: for men, > 14 drinks per week or ≥ 5 drinks per occasion at least once per month over the past 12 months; for women, > 7 drinks per week or ≥ 4 drinks per occasion at least once per month over the past 12 months. A total of 274 participants will be randomized, 137 to each medication group.

Interested individuals will come in to the laboratory for a two-part in-person screening visit. Eligible participants will then be randomized to either the combination of VAR (1 mg twice daily) + NTX (50 mg once daily) or VAR (1 mg twice daily) + PLA. Medication will be titrated over a 14-day period. Participants will attend a brain imaging session and receive an individual counseling session during week 2 of the medication titration period and the quit date will be set for day 14 of the medication regimen. All participants will be instructed to continue the study medications for 12 more weeks (14 weeks total) and will return to the laboratory for follow-ups 2, 4, 6, 8, 10, 12, 16, and 26 weeks post quit date. Follow-up visits at weeks 2, 6 and 10 may take place over the telephone as needed. At each follow-up, participants will complete questionnaires, receive brief smoking cessation counseling according to practice guidelines and will be encouraged to complete the online "Rethinking Drinking" program developed by NIAAA. Smoking abstinence [verified by CO level; 149] and alcohol use will be measured at each in-person follow-up to test whether the combination of VAR + NTX is superior to monotherapy for smoking cessation and drinking reduction.

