7.4. Medication Titration/Stabilization Period

7.4.1. Randomization and Medication Titration Visit

Participants who are eligible after the medical screening visit will be scheduled to come into the lab to be randomized and start study medication. Subjects will be urn randomized to one of two medication groups. Urn randomization will be used to balance the two medication groups by gender, number of cigarettes per day, and drinks per drinking day. At this visit, a quit date will be set for day 14 of the medication titration/stabilization regimen.

Female participants will be asked about their menstrual cycle and reproductive status and will answer questions about hormonal responses and symptoms (see Schedule of Assessments). In addition, female participants of child-bearing potential will provide a saliva sample for testing of progesterone and estradiol levels and urine will be tested for surges in luteinizing hormone (LH).

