7.4.3. Initial Counseling Session

All subjects will receive one smoking cessation counseling session to take place during week 2 of the medication titration period. This session will last approximately 45 minutes, and will focus on preparation for the upcoming quit date.

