7.4.4. Brain Imaging Session

Participants found to be eligible for an MRI, as determined by the MRI Safety Screening form, will be asked to complete a brain imaging session after 9-12 days of taking the medication.

Participants will be asked to abstain from drinking alcohol prior to coming into the lab for the brain imaging session, which will be verified through a breathalyzer. Only participants with a blood alcohol concentration of zero will be allowed to complete the scanning visit. Female participants will be given a pregnancy test to make sure that they are not pregnant. We will also collect a urine sample on that day to verify compliance with the study medication. We will then ask participants to fill out a few questionnaires including information about your use of alcohol and tobacco.

After the initial questionnaires, participants will receive some training on how to complete questionnaires in the scanner. The scanning will be performed at the Brain Mapping Center or at the Center for Cognitive Neuroscience, both located on the UCLA campus. They will be asked to lie down on a padded table, with their head placed in the center of a large, metal doughnut-shaped magnet. While the machine is running, the participant will hear loud banging noises and will be offered earplugs to reduce the noise made by the magnet. Head and back support will also be provided to minimize discomfort. In the scanner, participants will watch brief videos of individuals smoking cigarettes or performing daily activities, such as driving and will view alcohol and neutral cues. They will also be asked to rate their urge to smoke cigarettes and drink after watching each of these videos and visual cues.

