Combining Varenicline and Naltrexone for Smoking Cessation and Drinking Reduction

DATA ANALYSIS PLAN

NCT02698215

October 2018

Analyses were conducted in SAS Statistical Software Version 9.4. All analyses were of the intention-to-treat type. Since all participants took the first dose of the study medication under observation during the randomization visit, all participants were included in the subsequent analyses. The dichotomous primary outcome for smoking cessation at the 26-week follow up was analyzed using a Chi-Square test comparing smoking cessation rates for the two medication conditions. For the purpose of these analyses, all individuals who dropped out from the trial were considered to have returned to smoking, per guidelines for smoking cessation trials. For the drinking outcomes, all of which were continuous, a series of multilevel models, via Proc Mixed, were conducted for each outcome separately, during the 12-week treatment period and for the entire 26-weeks of the trial, which is consistent with pharmacotherapy trials for excessive drinking. These models tested whether the two medication groups differed in alcohol use over the 12-week medication period and across the entire 26-weeks of the trial. All models for drinking outcomes controlled for baseline drinking levels.

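### In the supplied text, women who are not scanned have no scheduled pregnancy test between day 1 of drug and day 42; a dipstick at the week-2 counseling visit would cheaply shorten the gap

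*Protocol*

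**What the plan says.** Section 9.29 sets the timing of scheduled pregnancy testing, which "will be completed at the initial screening visit, the medication titration visit, and at the 4, 8 and 12 week follow up visits". Other sections add tests at medical screening (7.3.3), at imaging (7.4.4) and at post-quit weeks 16 and 26 (7.6).

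The clock starts at the titration visit. Section 7.4.1 has participants randomized and started on drug there, and the SAP confirms that "all participants took the first dose of the study medication under observation during the randomization visit". Section 7.4.1 also says that "a quit date will be set for day 14 of the medication titration/stabilization regimen", and section 4 counts follow-up weeks from that date.

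The contacts between titration and week 4 are:

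- **Week-1 call (7.4.2):** a physician telephone call, with no test.
- **Counseling (7.4.3):** "All subjects will receive one smoking cessation counseling session to take place during week 2 of the medication titration period". No pregnancy test is listed.
- **Imaging (7.4.4):** limited to "Participants found to be eligible for an MRI, as determined by the MRI Safety Screening form". As to timing, this group "will be asked to complete a brain imaging session after 9-12 days of taking the medication". Here a test is listed: "Female participants will be given a pregnancy test to make sure that they are not pregnant".
- **Post-quit week 2 (sections 4 and 7.5):** "Follow-up visits at weeks 2, 6 and 10 may take place over the telephone as needed". No pregnancy test is tied to this contact.

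Sections 7.7 and 7.8.1 require a woman who becomes pregnant to stop study medication, and 7.8.1 notes that both drugs are Pregnancy Category C.

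**The concern.** The stopping rule for pregnancy works only once the pregnancy is known. In the text supplied, the longest interval between scheduled tests is the first one on drug, and it covers the whole titration. Whether a woman has a test inside that interval depends on whether she can and does attend an MRI scan, which has nothing to do with her chance of being pregnant.

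The pregnancy most affected is one already begun but too early for a dipstick to show at titration. An unscanned woman in that position could take study drug, at full dose from day 8, until the week-4 test unless she reports the pregnancy herself. Every participant has a counseling session in medication week 2, so there is a natural place for an earlier test. The point is one of participant safety. It does not touch randomization, endpoints, power or analysis.

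**Working it through.** The plan gives no figure of its own for these intervals, so the check is calendar arithmetic.

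**Inputs.** Day 1 is the titration visit and first dose (7.4.1, SAP). The quit date is day 14 (7.4.1). Follow-up week w falls on day 14 + 7w (section 4). Full dose runs from day 8 (7.4.1.1). Medication week 2 is days 8 to 14.

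**Test days on drug, unscanned women.**

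- Week 4: 14 + 28 = day 42
- Week 8: 14 + 56 = day 70
- Week 12: 14 + 84 = day 98
- Gaps: 42 − 1 = **41 days**; 70 − 42 = 28; 98 − 70 = 28

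Counting full dose only, days 8 to 41 are 34 days, which is 34 − 28 = 6 more than a later interval.

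**Scanned women.** A test on day 9 to 12 leaves 42 − 9 = 33 down to 42 − 12 = 30 days to week 4. If imaging after 12 days of drug is taken to mean day 13, the lower figure is 29.

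**With a counseling dipstick on day t (8 to 14).**

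| t | day 1 to t | t to day 42 | longest on-drug gap |
|---|---|---|---|
| 8 | 7 | 34 | 34 |
| 14 | 13 | 28 | 28 |

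The longest gap is **28 to 34 days**, about what scanned women have. A pregnancy whose dipstick first turns positive between day 2 and day t would be picked up by scheduled testing 42 − t = 28 to 34 days sooner.

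**What the added test does not do.** Let L be the lag from conception to a positive dipstick. The documents give no value; I assume 10 to 14 days.

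- *Conceptions it catches* run from day 2 − L (day −8 to day −12) to day t − L, at the latest 14 − 10 = day 4. They lie mostly before dosing.
- *Worst case left over* is a dipstick that turns positive on day t + 1, with conception on day t + 1 − L. For t = 14 and L = 10, conception is on day 5 and exposure covers days 5 to 41, which is 37 days. For t = 14 and L = 14, conception is on day 1 and exposure is days 1 to 41, which is 41 days. For t = 8 and any L from 10 to 14, conception precedes dosing and exposure is again 41 days.
- *Without the added test* the worst case is also 41 days, so the improvement there is 41 − 41 = 0 to 41 − 37 = 4 days.

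**The case against.** The strongest objection is that the controlling schedule is out of sight. Section 9 says assessments follow Appendix 2, of which only the title was supplied. Section 9.29 is plainly not a full list, since it omits the tests in 7.3.3, 7.4.4 and 7.6, so its silence on a further test is weak evidence that none exists. This stands, and it makes the point conditional.

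A reader might infer that a pregnancy missed at titration would go unnoticed until day 42. The documents do not support that. The exclusion criteria (7.2.2) recognize self-report. Before day 42 a woman has the week-1 physician call, the counseling session and the post-quit week-2 contact. Adverse events are asked about at study visits, and a 24-hour line to the physician is available (8.1). Only the timing of scheduled testing is at issue.

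A reader might also infer a breach of the monthly testing in 7.5. That section describes the follow-up period, and tests at weeks 4, 8 and 12 satisfy it. Nor does the reference in 7.2.2 to a positive test at any visit settle the matter the other way: it is an exclusion condition and schedules nothing.

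Finally, one might read the part of the 41-day interval that an earlier test covers as the share of pregnancies it would catch. It is only a share of calendar dates. Nothing in the documents says that pregnancies spread evenly over those dates, so it does not measure benefit.

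It is also fair that the imaging test is part of the scan visit and is not presented as a standard for monitoring drug exposure. Unscanned women are not deficient by comparison; the scanned schedule only shows what coverage is readily attainable.

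**Conclusion.** The point holds as a small, conditional safety improvement. On the supplied text, an unscanned woman has 41 days between scheduled pregnancy tests at the start of dosing, against 28 days later on; at full dose the excess is 6 days. No rule is broken. The risk is kept low by required contraception (7.2.2) and by tests at initial screening, medical screening and titration. The gain from an added test is earlier scheduled detection, by 28 to 34 days, of pregnancies too early to show at titration. Conceptions after titration will mostly still be missed by it, and worst-case exposure stays at 37 to 41 days under the assumed lag.

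The conclusion assumes that Appendix 2 has no test between titration and week 4, that visits fall on their nominal days, and that the counseling session is in person. Telephone is mentioned only for post-quit weeks 2, 6 and 10, and the compensation schedule (7.9) calls the counseling session a visit, but the text does not state outright that it is on site. The number of unscanned women is not given, so the number who would benefit is unknown.

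**What to change.** Check Appendix 2 first. If it already has a pregnancy test in medication week 2, only 9.29 needs a line to match.

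If it does not, add a urine pregnancy dipstick for women of child-bearing potential at the medication week-2 counseling visit, nearer day 14 where possible, and list it in 9.29 and Appendix 2. Women tested at imaging that week need no second test. Section 5.5.3 calls for a urine sample at each visit for the riboflavin check, so the same sample can serve.

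The cost is one dipstick per unscanned woman and one line in each of two places. If counseling is held by telephone for some women, they would need a separate sample. The SAP is written in the past tense; if dosing is already over, the change matters only for any later use of this schedule.
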